4.3.2.5. Virology analyses

Genotypic assessments will be analyzed separately by the study virologist. These analyses will be performed after SAC, when the genotypic data become available.

4.3.2.6. Immunology analyses

Change from baseline in CD4+, CD8+ and CD4+/CD8+ (if collected) will be summarized descriptively at every assessment visit. Visits up to Day 10 (inclusive) will exclude any values assessed under SoC, if SoC starts earlier for any reason.

To further explore the relationship between VH4524184 exposures and CD4+ T-cell counts, a scatter plot of change from baseline on Day 10 (within the monotherapy period) in CD4+ counts and Cmax after each administration, AUC₀₋₁₀ and C₁₀ will be created for all participants receiving active drug. A LOWESS line will be included in the scatter plot.

Further analyses may be conducted post SAC if any signals or trends are identified in this univariate analysis.

4.4. Tertiary Endpoints Analyses

4.4.1. Vital Signs

Post-baseline values of vital signs (temperature, systolic and diastolic blood pressure, pulse rate and respiratory rate) and change from baseline over time will be summarized by assessment visit.

The number of participants with worst case vital sign results relative to Potential Clinical Importance (PCI) criteria which are post-baseline relative to baseline will be summarized.

The change categories for PCI criteria are: To Low, To w/in Range or No Change, To High. The categorization is determined by comparing the baseline category to the worst case post-baseline category. The determination of the worst case post-baseline takes into account both planned and unscheduled assessments. Participants with missing baseline value are to be assumed to have a within range baseline value.

This summary will be produced while participants are under the monotherapy period, as well as overall (i.e. monotherapy + follow-up).

All vital signs data for participants with at least one value of potential clinical importance will be included in RAPIDO DV. PCI values for vital signs are defined in section [6.2.1](#).

4.4.2. ECG

If multiple ECG records are available for a visit/timepoint (e.g. in case of triplicate ECG), then the average for continuous ECG variables and the worst case for categorical will be used for data summaries for that visit/timepoint.

Post-baseline values of ECG parameters (heart rate, PR, QRS, QT, and QTc intervals) and change from baseline will be summarized by assessment visit.

The number and percentage of participants with ECG findings will be summarized by assessment visit. The ECG findings to be summarized are the ECG interpretation and clinical significance (yes/no) of abnormal ECGs. All ECG data for participants with a value of potential clinical importance occurring during either the monotherapy or follow-up period will be included in RAPIDO DV. PCI values for ECG parameters are defined in section [6.2.1](#).

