3. OBJECTIVES, ENDPOINTS AND ESTIMANDS

Table 3 Objectives and Endpoints

Objective(s)	Endpoint(s)
Primary	

 To evaluate the antiviral activity of orally administered VH4524184 in TN participants with HIV-1 during 10 days of monotherapy 	
 Maximum change from baseline (Day 1) in plasma HIV-1 RNA through Day 10.
Secondary	

 To assess the safety and tolerability of orally administered VH4524184 	
 Incidence of AEs, severity of AEs and proportion of participants who discontinue treatment due to AEs Change from baseline and maximum toxicity grade increase from baseline for liver panel laboratory parameter (ALT, AST, total bilirubin, direct bilirubin, alkaline phosphatase, albumin and total protein)

 To characterize the pharmacokinetic profile of orally administered VH4524184 	As data permits, PK measures that include: 
 Cmax, tmax Concentration on Day 10

 To evaluate any relationship between VH4524184 exposure and change in plasma HIV-1 RNA 	
 Correlation of VH4524184 PK parameters with maximum plasma HIV-1 RNA change from baseline through Day 10

 To assess the occurrence of emergent genotypic or phenotypic resistance after 10 days of monotherapy with VH4524184 	
 Genotypic and phenotypic data from baseline (Day 1) and Day 10 will be compared for amino acid substitutions and VH4524184 fold change IC50.

 To assess the immunologic effects of VH4524184 when administered over 10 days in participants living with HIV 	
 Change from baseline in CD4+ T-cell count to Day 10
Tertiary	

 To further assess the safety and tolerability of orally administered VH4524184 	
 Post baseline values and changes over time of vital signs, ECG parameters and suicidality scores. Absolute values, change from baseline and maximum toxicity grade increase from baseline for hematology, coagulation and remaining chemistry panels

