4.3.2.2. Liver panel laboratory analyses

Change from baseline values for liver panel laboratory parameters will be summarised by assessment visit. Visits up to Day 10 (inclusive) will exclude any liver panel values assessed under SoC, if SoC starts earlier for any reason, in line with the Estimand definition (section 1.1).

Laboratory toxicities will be graded according to the DAIDS Criteria Version 2.1. For liver panel lab tests that are gradable by DAIDS (e.g. ALT, AST), summary of worst-case grade increase from baseline grade will be provided. This summary will display the number and percentage of participants with a maximum post-baseline grade increase from their baseline grade. Also, maximum increase subtotals (i.e. max increase in grade to any grade between 1 and 4, max increase to grade 2-4 or max increase to grade 3-4) will be included. The grade increases are determined by comparing the baseline grade to the worst-case post-baseline grade (e.g., Increase to Grade 1, Increase to Grade 2 etc.) and maximum grade increase subtotals (e.g., Increase to Grades 1 to 4, Increase to Grades 2 to 4, Increase to Grades 3 to 4). The grading subtotals are determined by adding the counts for each worst-case grade change within the subtotal category, e.g., 'Increase to Grades 1 to 4' is a subtotal of all worst-case increases to Grade 1, to Grade 2, to Grade 3, and to Grade 4. Participants with missing baseline value are to be assumed to have a Grade 0 at baseline. The determination of the worst case during the post-baseline period takes into account both planned and unscheduled assessments. This summary will be produced while participants are under the monotherapy period, as well as overall (i.e. monotherapy + follow-up).

For lab tests that are not gradable by DAIDS, summaries of worst-case changes from baseline with respect to normal range will be generated. Decreases to low, changes to normal or no changes from baseline, and increases to high will be summarized for the worst-case post-baseline. If a subject has a decrease to low and an increase to high during the same time interval, then the subject is counted in both the "Decrease to Low" categories and the "Increase to High" categories.

Liver panel data for participants with at least one abnormal lab value will be included in the listing of chemistry laboratory parameters.

More details of all planned displays are provided in the OPS document.

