4.4.4. Hematology, coagulation, urinalysis and remaining chemistry lab parameters

Post-baseline values, change from baseline and maximum toxicity grade increase from baseline for hematology, coagulation, urinalysis and remaining chemistry panels will follow the same approach as liver panel laboratory analyses, detailed in section [4.3.2.2](#).

There are some lab parameters which are graded for both low values and high values. Summaries of these lab tests will be differentiated by term, e.g. sodium will be

summarized as “hyponatremia” and “hypernatremia”, calcium as “hyperkalemia” and “hypokalemia” etc.

For urinalysis parameters assessed with the dipstick method, summaries of worst-case post-baseline relative to baseline will be created. The categories for which summaries (i.e. number and percentage of participants) will be provided are based on the actual values within the data, e.g. ‘No Change/Decreased’, ‘Increase to TRACE’, ‘Increase to 1+ or Increase to +’, ‘Increase to 1+ or to 1/4 G/DL’, etc. ‘Decreased’ indicates a “lesser” result including change to a negative result. The categorization is determined by comparing the baseline category to the worst-case post-baseline category. The determination of the worst-case post-baseline takes into account both planned and unscheduled assessments. Subjects with a missing baseline value are to be assumed to have a negative baseline value.

These summaries will be produced while participants are under the monotherapy period, as well as overall (i.e. monotherapy + follow-up).

A listing of hematology, coagulation and chemistry laboratory data will be created. For each laboratory category (i.e. chemistry, hematology etc.), the listing will include participants with at least one abnormal lab value (i.e. DAIDS grade ≥ 1 for graded parameters or outside normal range for non-graded) during either the monotherapy or the follow-up period in any lab parameter within a lab category. All data for all lab parameters within the lab category in which an abnormal value was observed will be included in the listing; no lab parameters from another lab category in which no abnormal values were observed will be included (e.g. if a participant has an abnormal ALT value then all data from all chemistry lab parameters will be included in the listing and none of the lab parameters from hematology and coagulation).

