6.2. Appendix 2 Data Derivations Rule

6.2.1. Criteria for Potential Clinical Importance

Reference ranges for all laboratory parameters collected throughout the study are provided by the laboratory. A laboratory value that is outside the reference range is considered either high abnormal (value above the upper limit of the reference range) or low abnormal (value below the lower limit of the reference range). A high or low abnormal laboratory value is not necessarily of clinical concern.

The Division of AIDS (DAIDS) grading for severity of laboratory toxicities and clinical adverse events, version 2.1, July 2017 will be used to assign grades to laboratory values as specified in the protocol.

In addition, the following criteria will be used to flag potential clinical importance:

ECG Parameter	Units	Clinical Concern Range	
		Lower	Upper
Absolute			
Absolute QTc Interval (QTcF)	msec	< 320	> 450 (Males) > 470 (Females)

Change from Baseline		
Increase from baseline QTc	Msec	> 60*

*On-treatment triplicate averaged QTcF value > 60 msec over baseline regardless of sex

Vital Sign Parameter	Units	Clinical Concern Range	
		Lower	Upper
Absolute			
Systolic Blood Pressure	mmHg	< 85	> 140
Diastolic Blood Pressure	mmHg	< 45	> 90
Heart Rate	bpm	< 45 (Males) < 50 (Females)	> 100

Note: PCI values for Respiratory Rate & Temperature are not applicable.

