6.2.4. Assessment Window

For data summaries by visit, the nominal visit description will be used. Unscheduled and withdrawal visit data will be slotted into a target visit based on visit window defined in the table below. Within each study period, if there are multiple assessments within the same window, the following hierarchy will determine which assessment will be used:

1. The assessment that is closest to the target day.
2. If there are multiple assessments equidistant from the target day, then:
 - a. For continuous parameters, the average of the values will be used
 - b. For categorical parameters, the worst assessment will be used

CCI

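### SAP 4.4.2 tabulates ECG by visit only, so no planned table counts participants whose worst QTcF, unscheduled readings included, exceeds a limit

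*SAP*

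**What the plan says.** Protocol Table 3 puts vital signs and ECG in one tertiary endpoint: "Post baseline values and changes over time of vital signs, ECG parameters and suicidality scores".

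SAP 4.4.2 plans two ECG summaries. The first is "Post-baseline values of ECG parameters (heart rate, PR, QRS, QT, and QTc intervals) and change from baseline will be summarized by assessment visit". The second, of ECG interpretation and clinical significance, is also by visit. The limits for potential clinical importance serve a different purpose there, which is to select whose records the viewer holds: "participants with a value of potential clinical importance occurring during either the monotherapy or follow-up period will be included in RAPIDO DV".

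SAP 6.2.1 sets those limits. QTcF is flagged below 320 msec, above 450 msec (males) or 470 msec (females), and for a rise of more than 60 msec, footnoted as "On-treatment triplicate averaged QTcF value > 60 msec over baseline regardless of sex".

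For vital signs, SAP 4.4.1 goes further. It counts participants by worst post-baseline category against the 6.2.1 criteria, for monotherapy and overall, and states: "The determination of the worst case post-baseline takes into account both planned and unscheduled assessments".

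SAP 6.2.4 slots unscheduled data into visit windows for by-visit tables. If several readings share a window, the first choice is: "The assessment that is closest to the target day". Readings equally distant from the target day are averaged if continuous.

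**The concern.** Two measures share an endpoint and a table of limits, but only one gets a count against its limits. The SAP gives no reason.

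The QTcF thresholds matter in the conduct of the study. Protocol 7.1.3 withdraws a participant from treatment for QTcF above 500 msec or a rise above 60 msec, on averaged triplicates. Under Protocol 8.3.7, one such participant pauses the study if the investigator considers the event reasonably attributable to the drug. Protocol 8.3.3 foresees extra ECGs when clinically indicated, and these are the readings most likely to show prolongation. A by-visit summary that prefers the reading nearest the target day is poorly suited to capturing them.

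At stake is a plain safety statement in the study report: how many participants in each dose group ever exceeded a QTcF limit, out of how many with a post-dose ECG.

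**Working it through.** The documents give no figure to reproduce. The check is a comparison of text, followed by an illustration of the selection rule.

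**1. The two sections compared**

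| Feature | Vital signs (SAP 4.4.1) | ECG (SAP 4.4.2) |
|---|---|---|
| Same tertiary endpoint (Protocol Table 3) | Yes | Yes |
| Limits in SAP 6.2.1 | Yes | Yes (QTcF) |
| Values and change by visit | Yes | Yes |
| Count by worst post-baseline category | Yes | No |
| Unscheduled readings counted towards the worst case | Yes | No such table |
| Use made of the limits | Table and viewer | Viewer only |

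The only worst-case wording in SAP 4.4.2 concerns categorical ECG variables with several records at one visit or timepoint. It does not work across visits.

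**2. What SAP 6.2.4 can do to a reading**

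The values here are assumed, for illustration: baseline QTcF 425 msec, 430 msec on the target day, and an unscheduled 505 msec one day later in the same window and study period.

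- Closest reading kept: 430 − 425 = +5 msec.
- Worst reading: 505 − 425 = +80 msec, above both the 500 and the +60 limits.
- If the two were instead equidistant from the target day, they would be averaged: (430 + 505)/2 = 467.5 msec, and 467.5 − 425 = +42.5 msec, below both limits.

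The loss needs a second reading in the same window. A lone unscheduled reading is kept and enters its visit row. The windows themselves are redacted, so how often two readings would compete is unknown.

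**3. What the by-visit rows give when nothing is lost**

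SAP 4.1.1 supplies n, minimum and maximum for each row. Three things remain unavailable:

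- *Distinct participants.* A maximum shows that at least one value is high. It does not show whether one or two participants exceeded the limit, or whether high values at two visits come from the same person.
- *The sex-specific limit.* A row maximum of, say, 460 msec exceeds the limit for a male (450) but not for a female (470). A pooled row cannot say which.
- *The denominator.* Per-visit n does not give the number of distinct participants with at least one post-dose ECG.

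**4. Scale**

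Each Part 1 cohort has 6 active participants, so one case is 1/6 = 16.7% of a dose group.

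**The case against.** The strongest reply is that this asks for one more tertiary table when the endpoint is already met. Most of that stands. The endpoint wording asks for values and changes over time, and by-visit tables provide them. In groups of 6, the row maximum normally reveals the outlier.

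Serious cases also surface elsewhere. Protocol 7.1.3 makes new clinically relevant ECG findings adverse events, Protocol 10.6.2 grades QTcF prolongation, and SAP 4.3.2.1 tabulates adverse events by maximum grade. A case that stops treatment appears among the discontinuation reasons in SAP 6.1.1. These routes are good but incomplete. Adverse event reporting depends on the investigator's judgement of relevance. Under Protocol 7.1, discontinuation means not receiving all planned doses, so prolongation found after the last dose cannot appear there. RAPIDO DV is an interactive participant-level viewer, not a summary by dose group.

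A reader might also draw stronger conclusions, which the documents do not support:

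- *That no ECG is planned between Day 1 and Day 38.* Part of the ECG note in Protocol Table 1 is redacted, so the schedule cannot be judged. Nor can a bound on the risk be calculated, because the number of participants with a post-dose monotherapy ECG is not given.
- *That the report could not distinguish no prolongation from few ECGs taken.* The n in each visit row largely answers this.
- *That ECG is the one safety domain denied a worst-case table.* The liver and other laboratory sections do include unscheduled values ("The determination of the worst case during the post-baseline period takes into account both planned and unscheduled assessments"; "The determination of the worst-case post-baseline takes into account both planned and unscheduled assessments"). But the protocol endpoints for the liver, hematology, coagulation and chemistry panels name the maximum toxicity grade increase, and the ECG endpoint names no maximum. Suicidality, in the same endpoint line as ECG, has no post-baseline worst-case table in SAP 4.4.3 either. Vital signs are the fair comparator.
- *That the footnote to the 60 msec flag conflicts with the use of flags in follow-up.* The absolute limits still apply there, and the triplicate basis matches Protocol 7.1.3.

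**Conclusion.** The point holds as a small gap in safety reporting. As the SAP is written, ECG is tabulated by visit only, a prolonged unscheduled QTcF can be displaced when it shares a window with a reading nearer the target day, and no table counts distinct participants over a QTcF limit. The SAP's own method for vital signs would close the gap.

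Importance is low. The endpoint is tertiary and descriptive, and no decision rule uses the missing count. Participants with cardiac disease, a long-QT history or a need for QT-prolonging drugs are excluded. Protocol 4.3 plans exposures below those in study 218803, where Protocol 2.2.1.1 reports no ECG trends. The by-visit table meets the protocol endpoint, so this is an optional improvement, not a conflict with the protocol.

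The conclusion rests on SAP 4.4.2 being the full account of planned ECG tables. The OPS, which holds display details, was not supplied and may already contain such a table. The displacement also depends on two readings sharing a window, which the redacted windows do not allow anyone to quantify.

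**What to change.** Add one table to SAP 4.4.2, by dose group with pooled placebo as in SAP 4.1.1, for monotherapy and overall:

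- Denominator: participants with at least one post-dose ECG in the period.
- Counts: participants whose worst post-baseline QTcF is above 450 msec (males) or 470 msec (females), above 500 msec, or more than 60 msec above baseline.
- Source: planned and unscheduled ECGs, as in SAP 4.4.1, without the one-reading-per-window selection of SAP 6.2.4.
- Readings: the triplicate average where one exists; mark counts that rest on a single reading.

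The cost is one table from data already collected and a few lines of SAP text before database lock, with no added visit, procedure or sample. The downside is one more low-importance tertiary display. If the OPS already holds it, only a sentence in SAP 4.4.2 is needed.

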4.4.3. Suicidality Scores

Baseline suicidality data assessed electronically via the C-SSRS questionnaire will be summarised. Number and percentage of participant with suicidal ideation or behaviour during lifetime and currently (i.e. within the past 2 months of screening) will be presented.

Participant-level suicidality data will be available via RAPIDO DV.

4.4.4. Hematology, coagulation, urinalysis and remaining chemistry lab parameters

Post-baseline values, change from baseline and maximum toxicity grade increase from baseline for hematology, coagulation, urinalysis and remaining chemistry panels will follow the same approach as liver panel laboratory analyses, detailed in section [4.3.2.2](#).

There are some lab parameters which are graded for both low values and high values. Summaries of these lab tests will be differentiated by term, e.g. sodium will be

summarized as “hyponatremia” and “hypernatremia”, calcium as “hyperkalemia” and “hypokalemia” etc.

For urinalysis parameters assessed with the dipstick method, summaries of worst-case post-baseline relative to baseline will be created. The categories for which summaries (i.e. number and percentage of participants) will be provided are based on the actual values within the data, e.g. ‘No Change/Decreased’, ‘Increase to TRACE’, ‘Increase to 1+ or Increase to +’, ‘Increase to 1+ or to 1/4 G/DL’, etc. ‘Decreased’ indicates a “lesser” result including change to a negative result. The categorization is determined by comparing the baseline category to the worst-case post-baseline category. The determination of the worst-case post-baseline takes into account both planned and unscheduled assessments. Subjects with a missing baseline value are to be assumed to have a negative baseline value.

These summaries will be produced while participants are under the monotherapy period, as well as overall (i.e. monotherapy + follow-up).

A listing of hematology, coagulation and chemistry laboratory data will be created. For each laboratory category (i.e. chemistry, hematology etc.), the listing will include participants with at least one abnormal lab value (i.e. DAIDS grade ≥ 1 for graded parameters or outside normal range for non-graded) during either the monotherapy or the follow-up period in any lab parameter within a lab category. All data for all lab parameters within the lab category in which an abnormal value was observed will be included in the listing; no lab parameters from another lab category in which no abnormal values were observed will be included (e.g. if a participant has an abnormal ALT value then all data from all chemistry lab parameters will be included in the listing and none of the lab parameters from hematology and coagulation).

A listing of urinalysis data will be created. The urinalysis listing will include only participants with at least one abnormal value (i.e. outside normal range) for specific gravity or pH or if there is an increase from Baseline in Protein or in Occult Blood or if microscopy is performed, during either the monotherapy or the follow-up period.

4.5. Other Safety Analyses

Other safety analyses will be based on the Safety Analysis Set, unless otherwise specified.

4.5.1. Extent of Exposure

Extent of exposure in cumulative actual dose (mg) will be summarized and exposure will be listed for all participants.

